5.2 Handling of Study Interventions

Participants will be blinded to whether they are receiving the intervention or comparison group. The treatment protocol derives its theoretical framework from the Bodymind model of AT⁶² and from the application of Focusing to Art Therapy^{64,65} for the purpose of body awareness and developing a focusing (“being friendly, accepting, non-judgmental and welcoming to one’s inner felt sense”)⁶⁶. All sessions start with a ten-minute rapport building and touching base and continue with 50 minutes of art making in a calm and supportive environment. Art materials are on the table and after the art therapist provides a brief explanation of the use of the materials; participants are encouraged to explore and experience as they wish. Group leader is present to guide and assist. The role of the art therapist is to encourage a non-judgmental and exploratory approach to artmaking in which the process is emphasized over product. The art therapist obtains these goals by creating an atmosphere that is calm and by remaining tuned in to the verbalizations and body language of participants. If needed she can provide individual attention that is geared toward neutralizing concerns regarding performance during the art making. This approach is defined as providing a “Third-hand”⁶⁷: assisting in problem solving and dilemmas related to the

[figure not shown]

Figure 1: Flow chart of time-points

art making process. The art therapist encourages participants to refrain from conversation and instrumental music is played to encourage introspective experiences. The session ends with 30 minutes of processing and discussion in which the art therapist requests each participant to share and briefly presents their work and group participants can respond and or provide support. The art therapist will remind group members to be respectful and non-judgmental toward other participants and themselves.

Session 1: getting familiar and safe: An introduction to the group, the group leader will speak about motivation for exploration via art and remaining open to new experiences. The leader will introduce the art materials and art making from a non-judgmental stance and the importance of process of product. The concept of safe place will be introduced to the group and members will be asked to create a safe place via art. The goals of this session: Rapport Building, Contract Building and getting familiar and comfortable with the art materials.

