6.2.2 Enrollment, Baseline, and/or Randomization

Enrollment

Enrollment date is considered immediately following the signing of the consent form after which the enrollment date is recorded in the case book. The participant will be scheduled for a baseline visit in which she will be requested to fill out the baseline questionnaires and provide half an hour of baseline HR and Respiration measurements and 10 ccs of blood. Following this session, the participant will be randomized to the intervention or comparison group.

Baseline Assessments Visit 1 day 0- can be split in to 2 visits to reduce patient burden (see study schema- figure 1)

T1A

DEMOGRAPHICS AND TRADITIONALISM

- A.** We will be collecting baseline demographic data (age, marital status, children (if yes, and how many), religion, religiosity, education, employment, residence (city, village, etc).
- B.** We will measure ethnocultural differences using the Portrait Values Questionnaire (PVQ-RR), which is a 57-item scale consisting of items designed to measure 19 cultural values⁴³. The scale has been validated in 15 samples across 10 countries (n=6059) including Israel. The mean Cronbach α for the tradition values (which we will use as a covariate to enrich the ethno-cultural differences between Jews and Arabs, was 0.8343.

C. CHOLINERGIC ANTI-INFLAMMATORY PATHWAY

A. HRV: 20 minutes of resting ECG data will be recorded. The participants will be given instructions not to drink coffee or smoke for several hours before the lab visit as well as to sit quietly without talking or moving during the ECG recording.

B. Inflammation: We will collect 10 cc's of blood in order to measure immune dysregulation (pro-inflammatory cytokines IL-6, IL-8, IL-1 β , TNF- α), anti-inflammatory (IL-4, IL-10) and regulatory cytokine (TGF- β).

D. PATIENT REPORTED OUTCOMES (PRO):

A. Depression: The **Center for Epidemiologic Studies-Depression (CES-DR)** scale^{71- 10} ITEM SCALE.

B. Fatigue will be assessed using the Fatigue Symptom Inventory (**FSI**)⁷².

C. Pain: The **Breast Cancer Prevention Trial (BCPT) Symptom Scales**⁷³. The **PROMIS Pain Impact Scale**⁷⁴ measures how much pain interfered with different aspects of life in the past 4 weeks.

T1B

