A. The **Levels of Emotional Awareness Scale** is a written performance index of variation in the differentiation and complexity of emotional words used to answer the question “how would you feel and how would the other person feel” when presented with 10 evocative scenarios⁷⁵.

B. **Emotional Approach Coping** scales (e.g., **emotional processing, emotional expression**⁷⁶) and **COPE avoidance-oriented coping** subscales (e.g., denial, mental disengagement⁷⁷), all completed with reference to women’s experience of breast cancer.

C. The **Acceptance of Emotions Scale** assesses the extent to which subjects are accepting and nurturing toward their feelings²⁶.

B. Fatigue will be assessed using the Fatigue Symptom Inventory (**FSI**)⁷².

Randomization

Randomization will occur immediately following the baseline visit which will occur within 14 days of the screening visit and one week before the intervention begins. The University statistician will generate numbered envelopes to be opened consecutively as subjects enroll and the envelopes will designate individuals to the intervention through use of a random numbers table.

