6.2.4 T 2 – POST intervention

EMOTION PROCESSING

A. The **Levels of Emotional Awareness Scale** is a written performance index of variation in the differentiation and complexity of emotional words used to answer the question “how would you feel and how would the other person feel” when presented with 10 evocative scenarios ^{75,78}.

B. **Emotional Approach Coping** scales (e.g., **emotional processing, emotional expression** ^{79,80}) and COPE **avoidance-oriented coping** subscales⁷⁹ (e.g., denial, mental disengagement), all completed with reference to women’s experience of breast cancer.

C. The **Acceptance of Emotions Scale** assesses the extent to which subjects are accepting and nurturing toward their feelings²⁴.

D. PATIENT REPORTED OUTCOMES (PRO):

A. Depression: The **Center for Epidemiologic Studies-Depression (CES-DR)** scale^{71- 70} ITEM SCALE.

B. Fatigue will be assessed using the Fatigue Symptom Inventory (**FSI**)⁷².

C. Pain: The Breast Cancer Prevention Trial (BCPT) Symptom Scales⁷³. The PROMIS Pain Impact Scale⁷⁴ measures how much pain interfered with different aspects of life in the past 4 weeks.

CHOLINERGIC ANTI-INFLAMMATORY PATHWAY

A. HRV: 20 minutes of resting ECG data will be recorded. The participants will be given instructions not to drink coffee or smoke for 3 hours before the lab visit as well as to sit quietly without talking or moving during the ECG recording.

B. Inflammation: We will collect 10 ccs of blood in order to measure immune dysregulation (pro-inflammatory cytokines IL-6, IL-8, IL-1 β , TNF- α), anti-inflammatory (IL-4, IL-10) and regulatory cytokine (TGF- β).

T3-8 WEEKS AFTER END OF INTERVENTION Completion/Final Evaluation

CHOLINERGIC ANTI-INFLAMMATORY PATHWAY

A. HRV: 20 minutes of resting ECG data will be recorded. The participants will be given instructions not to drink coffee or smoke for 3 hours before the lab visit as well as to sit quietly without talking or moving during the ECG recording.

B. Inflammation: We will collect 10 ccs of blood in order to measure immune dysregulation (pro-inflammatory cytokines IL-6, IL-8, IL-1 β , TNF- α), anti-inflammatory (IL-4, IL-10) and regulatory cytokine (TGF- β).

D. PATIENT REPORTED OUTCOMES (PRO):

A. Depression: The **Center for Epidemiologic Studies-Depression (CES-DR)** scale^{71- 10} ITEM SCALE.

B. Fatigue will be assessed using the Fatigue Symptom Inventory (**FSI**)⁷².

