**NCT03377816: The Role of Emotional Processing in Improving the Quality of Life of
Breast Cancer Patients (REPAT)**

Statistical Analysis Plan- September 14th, 2017

The following statistical analysis plan was written in September of 2017 as part of the grant proposal for the REPAT study and was incorporated into the study protocol and guided the design of the actual study.

C.5 Statistical Methods:

C.5.1 Sample Size: A power analysis was conducted via Monte Carlo simulation in Mplus showed that a sample size of 240 (120 per condition), provides: (1) >90% power to detect a moderate effect size (Cohen's $d = 0.50$) of treatment on mechanisms, (2) >90% power to detect a moderate association ($r = 0.30$) between mechanisms and symptoms, and (3) >90% power to detect an indirect effect from treatment to symptoms via mechanisms. The sample size will also provide >80% power to detect a moderate effect size for the Condition by Ethno-Cultural group interaction.

C.5.2 Data Analysis: Prior to testing hypotheses, we will produce a thorough descriptive profile of the sample and examine the distributions of key variables involved in the hypotheses. We will also examine levels of nonresponse and **missing data**. Prior experience indicates attrition will be low; although, some missing data are expected due to missed assessments and dropout. Data will be analyzed using full information maximum likelihood to address missing data, supplemented with pattern-mixture modeling for non-random missingness. The first part of Hypothesis 1: women in the AT group experience greater increases in emotion processing, HRV, and regulatory cytokine levels and greater decreases in pro-inflammatory cytokines than women randomized to the Mandala condition will be tested using linear mixed models¹²⁹. Models will include a Time x Condition interaction to test whether the change over time in emotion processing and cholinergic anti-inflammatory processes is significantly different between treatment groups.

A significant interaction will be followed up by simple slope tests to characterize the degree of change separately in the AT and Mandala conditions.

The second part of Hypothesis 1: emotion processing and cholinergic anti-inflammatory processes mediate the effects of AT on symptoms (depression, pain, fatigue) will be tested using path analysis.

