Specifically, models will be tested where condition (AT versus Mandala) predicts the change in emotion processing or physiological correlates (path a) and the change in emotion processing or physiological correlates predicts the change in symptoms (path b). Mediation will be tested by calculating the indirect effect as the product of coefficients (path a x path b) and utilizing bootstrapping to calculate 95% confidence intervals and statistical significance¹³⁰.

Hypothesis 2: changes in emotion processing and cholinergic anti-inflammatory processes will be correlated and have unique effects will be tested by expanding the path analyses from Hypothesis 1 to simultaneously include all proposed mediators on each symptom outcome. Indirect effects with bootstrapped confidence intervals will be calculated as before. The change in mediators will be allowed to freely correlate to examine their relations.

[figure not shown]

Figure 3: Model hypotheses 1 & 2

The Exploratory Hypothesis posits a sequential mediation model from treatment (AT versus Mandala) to emotion processing (path a) to cholinergic anti-inflammatory processes (path b) and finally to symptoms (path c). To establish temporal precedence, change in emotion processing from baseline to intervention midpoint and change in cholinergic anti-inflammatory processes from intervention midpoint to completion, and change in symptoms from baseline to intervention completion will be used. Indirect effects will be calculated as the product of three coefficients (path a x path b x path c) capturing the hypothesized sequentially mediated effect. Bootstrapped confidence intervals and significance tests will be calculated. To test the reverse ordering, the same process will be used exchanging the time points and order of emotion processing and cholinergic anti-inflammatory processes.

[figure not shown]

Figure 4: Model Hypothesis 3

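### The exploratory sequential mediation model depends on an intervention-midpoint measurement that the readable schedule does not contain

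*SAP*

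**What the plan says.** SAP C.5.2, in the paragraph on the exploratory hypothesis, sets out a three-path chain: condition to emotion processing (a), emotion processing to HRV and cytokines (b), and these to symptoms (c). To put the links in time order it uses "change in emotion processing from baseline to intervention midpoint and change in cholinergic anti-inflammatory processes from intervention midpoint to completion". For symptoms, "change in symptoms from baseline to intervention completion will be used". For the opposite order, "the same process will be used exchanging the time points and order of emotion processing and cholinergic anti-inflammatory processes". The indirect effect is the product of the three coefficients, with bootstrap intervals. On missing values the SAP says: "Data will be analyzed using full information maximum likelihood to address missing data".

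The protocol text describes three measurement occasions:

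- Baseline (T1A/T1B, Protocol 6.2.2). It comes before allocation: "Randomization will occur immediately following the baseline visit".
- T2, after the intervention (Protocol 6.2.4).
- T3, headed "T3-8 WEEKS AFTER END OF INTERVENTION Completion/Final Evaluation" (also in 6.2.4).

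The protocol summary, under interventions and duration, adds only the follow-up at 8 weeks. Section 5.2 carries a figure captioned "Figure 1: Flow chart of time-points", to which 6.2.2 refers. Neither that figure nor SAP Figure 4 is shown in the copy reviewed.

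**The concern.** Both mediator changes begin or end at a point halfway through treatment, in both orderings, yet no readable section of the protocol measures either mediator then. A change score with one end unmeasured in every participant cannot be calculated.

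What is at stake is the claim about sequence. Hypotheses 1 and 2 relate changes to one another without any rule on which comes first; this is the one analysis built to address order. The SAP gives no alternative windows. If the midpoint does not exist, the analyst would have to pick substitutes after the data are in, across several mediators, three symptoms and two orderings, and the result could not be presented as pre-specified.

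**Working it through.** **1. The plan's own figures.** SAP C.5.1 states more than 90% power at 240 women (120 per arm) for d = 0.50, for r = 0.30 and for the simple indirect effect. With a two-sided 5% level (an assumption; the documents give none):

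- d = 0.50: Φ(0.50/√(2/120) − 1.96) = Φ(3.87 − 1.96) = 97.2%.
- r = 0.30: Φ(atanh(0.30) × √237 − 1.96) = Φ(4.76 − 1.96) = 99.7%.
- Simple indirect effect: about 96% (3,000 simulated trials, both paths significant).

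The stated power is reproduced, and none of it depends on a midpoint visit. No power is stated for the three-coefficient chain.

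**2. Occasions needed and described.** The model needs the mediators at baseline, midpoint and completion. The protocol text describes baseline, post-intervention and 8 weeks later. Midpoint occasions found: none for emotion processing, HRV or cytokines.

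**3. The table in Protocol 6.1.** It has 12 columns: screening (1), baseline (2), W1 to W9 (3 to 11) and W16 (12). Questionnaires and heart-rate measurement are marked at baseline, W8 and W9; blood at baseline and W8. For these three rows at W1 to W7, 0 of 3 × 7 = 21 cells are marked. Taking the midpoint as W4 (half of 8 weeks, an assumption), it is column 6, so the nearest marks are 6 − 2 = 4 and 10 − 6 = 4 columns away. A one-column misalignment would still leave W4 empty. This is supporting evidence only, because the table itself disagrees with 6.2.4: it marks only demographics at W16, while 6.2.4 collects questionnaires, HRV and blood at T3.

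**4. Change scores on the readable schedule.**

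| Ordering | Change score | Window | Can be formed? |
|---|---|---|---|
| Planned | Emotion processing | baseline to midpoint | no |
| Planned | HRV/cytokines | midpoint to completion | no |
| Planned | Symptoms | baseline to completion | yes |
| Reverse | HRV/cytokines | baseline to midpoint | no |
| Reverse | Emotion processing | midpoint to completion | no |
| Reverse | Symptoms | baseline to completion | yes |

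Two of three are missing in each ordering. Path a has a missing outcome, path b is missing at both ends, and path c has a missing predictor. No coefficient, and so no product, can be estimated as defined.

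**5. Missing-data method.** Full information maximum likelihood uses the observed values of a variable to handle gaps in it. A variable observed in nobody contributes no information, so the method does not rescue the model.

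**6. A limit of the design even with a midpoint.** Symptom change runs from baseline to completion and so spans the second mediator's window. Path c would not be time-ordered in any case.

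**The case against.** The strongest point is that the protocol's own time-point chart has not been seen and might show a midpoint. That stands, and the conclusion is conditional on it. The surrounding text nevertheless consistently describes three occasions. A midpoint shown only in the figure would conflict with 6.1 and 6.2, so a reconciliation would still be needed.

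One could also read completion as T3, since the T3 heading uses that word, and treat T2 as the midpoint. This does not stand: the SAP speaks of the midpoint and completion of the intervention, and T2 falls after the intervention.

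The analysis is exploratory, is not among the objectives in Protocol section 1 and has no stated power. That stands and limits the weight of the point. Against it, Protocol section 3 gives the effect of emotional processing on HRV and cytokines as a reason for the design, and that is path b.

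The SAP dates from the 2017 grant proposal, so the midpoint may be left over from another design. The documents do not say. The SAP states that it was incorporated into the protocol and guided the study, so its windows count as current.

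A reader might infer that no midpoint data exist, or that the mediation hypotheses fail as well. The documents support neither: the first cannot be settled without Figure 1 or study records, and Hypotheses 1 to 3 name no midpoint. Nor do the T0/T1/T2 labels on the appendix questionnaires prove the case, because they do not match the T1/T2/T3 numbering in the body.

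**Conclusion.** The SAP and the readable protocol do not agree. On the readable schedule, the exploratory sequential model cannot be run as specified in either ordering, for any of the 240 planned women, and the trial has no other analysis designed to show time order. This rests on the protocol text and, secondarily, on table 6.1; it would change if Figure 1 or study records show midpoint measurement of emotion processing, HRV and cytokines. Hypotheses 1 to 3 and the stated power are untouched. The point is worth fixing before analysis, but it does not threaten the main analyses.

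**What to change.** Before the data are analysed:

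1. Confirm from Figure 1 and study records whether emotion processing, HRV and cytokines are measured at a midpoint. If they are, correct Protocol 6.1 and 6.2 to show it and keep the model.
2. If they are not, amend the SAP in one of two ways:
   - Withdraw the temporal-precedence wording and report the chain on baseline-to-post changes as associational. This is the simpler repair.
   - Redefine the windows on existing occasions. For example, use first-mediator change T1 to T2, second-mediator change T2 to T3 and symptoms at T3, adjusted for condition and baseline values, with the mediators swapped for the reverse order.

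The second option requires 6.1 and 6.2.4 to be reconciled first on what is collected at T3, including blood. Cytokines should be dropped from any window without a blood sample. If T3 blood is not drawn, they leave the planned-order chain and the two orderings can be compared for HRV only. The SAP should then state that the model tests ordering after treatment and not during it, that the last path is contemporaneous, and that a null result would not refute the SAP's within-treatment hypothesis.

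The cost is SAP wording and a check of records, with no visit beyond those in 6.2.4. The downside is that, without a midpoint, the within-treatment ordering question is either given up or changed, and the analysis remains exploratory with no stated power.
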